15.2.2. Since Last Visit Version

COLUMBIA-SUICIDE SEVERITY RATING SCALE (C-SSRS)

Since Last Visit

Version 1/14/09

Posner, K.; Brent, D.; Lucas, C.; Gould, M.; Stanley, B.; Brown, G.; Fisher, P.; Zelazny, J.; Burke, A.; Oquendo, M.; Mann, J.

Disclaimer:

This scale is intended to be used by individuals who have received training in its administration. The questions contained in the Columbia-Suicide Severity Rating Scale are suggested probes. Ultimately, the determination of the presence of suicidal ideation or behavior depends on the judgment of the individual administering the scale.

Definitions of behavioral suicidal events in this scale are based on those used in The Columbia Suicide History Form, developed by [name] and [name], Conte Center for the Neuroscience of Mental Disorders (CCNMD), New York State Psychiatric Institute, [name]. (Oquendo M. A., Halberstam B. & Mann J. J., Risk factors for suicidal behavior: utility and limitations of research instruments. In M.B. First [Ed.] Standardized Evaluation in Clinical Practice, pp. 103 -130, 2003.)

For reprints of the C-SSRS contact [name]., New York State Psychiatric Institute, [name]; inquiries and training requirements contact [contact]

© 2008 The Research Foundation for Mental Hygiene, Inc.

SUICIDAL IDEATION		Since Last Visit						

Ask questions 1 and 2. If both are negative, proceed to "Suicidal Behavior" section. If the answer to question 2 is "yes", ask questions 3, 4 and 5. If the answer to question 1 and/or 2 is "yes", complete "Intensity of Ideation" section below.
								

1. Wish to be Dead Subject endorses thoughts about a wish to be dead or not alive anymore, or wish to fall asleep and not wake up. Have you wished you were dead or wished you could go to sleep and not wake up?
 
If yes, describe:
		Yes  No 						

2. Non-Specific Active Suicidal Thoughts General non-specific thoughts of wanting to end one's life/commit suicide (e.g., "I've thought about killing myself") without thoughts of ways to kill oneself/associated methods, intent, or plan during the assessment period. Have you actually had any thoughts of killing yourself?
 
If yes, describe:
		Yes  No 						

3. Active Suicidal Ideation with Any Methods (Not Plan) without Intent to Act Subject endorses thoughts of suicide and has thought of at least one method during the assessment period. This is different than a specific plan with time, place or method details worked out (e.g., thought of method to kill self but not a specific plan). Includes person who would say, "I thought about taking an overdose but when, where or how I would actually do it.....and I would never go through with it". Have you been thinking about how you might do this?
 
If yes, describe:
		Yes  No 						

4. Active Suicidal Ideation with Some Intent to Act, without Specific Plan Active suicidal thoughts of killing oneself and subject reports having some intent to act on such thoughts, as opposed to "I have the thoughts but I definitely will not do anything about them". Have you had these thoughts and had some intention of acting on them?
 
If yes, describe:
		Yes  No 						

5. Active Suicidal Ideation with Specific Plan and Intent Thoughts of killing oneself with details of plan fully or partially worked out and subject has some intent to carry it out. Have you started to work out or worked out the details of how to kill yourself? Do you intend to carry out this plan?
 
If yes, describe:
		Yes  No 						
INTENSITY OF IDEATION								

The following features should be rated with respect to the most severe type of ideation (i.e., 1-5 from above, with 1 being the least severe and 5 being the most severe).
 
Most Severe Ideation: _____
		Most Severe						

Frequency How many times have you had these thoughts?
 
(1) Less than once a week (2) Once a week (3) 2-5 times in week (4) Daily or almost daily (5) Many times each day
		_____						

Duration When you have the thoughts how long do they last?
 
 
 (1) Fleeting - few seconds or minutes	(4) 4-8 hours/most of day	
 
 (2) Less than 1 hour some of the time	(5) More than 8 hours/persistent or continuous	
 
 (3) 1-4 hours a lot of time		
 
		(1) Fleeting - few seconds or minutes	(4) 4-8 hours/most of day	(2) Less than 1 hour some of the time	(5) More than 8 hours/persistent or continuous	(3) 1-4 hours a lot of time		_____
(1) Fleeting - few seconds or minutes	(4) 4-8 hours/most of day							
(2) Less than 1 hour some of the time	(5) More than 8 hours/persistent or continuous							
(3) 1-4 hours a lot of time								

Controllability Could/can you stop thinking about killing yourself or wanting to die if you want to?
 
 
 (1) Easily able to control thoughts	(4) Can control thoughts with a lot of difficulty	
 
 (2) Can control thoughts with little difficulty	(5) Unable to control thoughts	
 
 (3) Can control thoughts with some difficulty	(0) Does not attempt to control thoughts	
 
		(1) Easily able to control thoughts	(4) Can control thoughts with a lot of difficulty	(2) Can control thoughts with little difficulty	(5) Unable to control thoughts	(3) Can control thoughts with some difficulty	(0) Does not attempt to control thoughts	_____
(1) Easily able to control thoughts	(4) Can control thoughts with a lot of difficulty							
(2) Can control thoughts with little difficulty	(5) Unable to control thoughts							
(3) Can control thoughts with some difficulty	(0) Does not attempt to control thoughts							

Deterrents Are there things - anyone or anything (e.g., family, religion, pain of death) - that stopped you from wanting to die or acting on thoughts of committing suicide?
 
 
 (1) Deterrents definitely stopped you from attempting suicide	(4) Deterrents most likely did not stop you	
 
 (2) Deterrents probably stopped you	(5) Deterrents definitely did not stop you	
 
 (3) Uncertain that deterrents stopped you	(0) Does not apply	
 
		(1) Deterrents definitely stopped you from attempting suicide	(4) Deterrents most likely did not stop you	(2) Deterrents probably stopped you	(5) Deterrents definitely did not stop you	(3) Uncertain that deterrents stopped you	(0) Does not apply	_____
(1) Deterrents definitely stopped you from attempting suicide	(4) Deterrents most likely did not stop you							
(2) Deterrents probably stopped you	(5) Deterrents definitely did not stop you							
(3) Uncertain that deterrents stopped you	(0) Does not apply							

Reasons for Ideation What sort of reasons did you have for thinking about wanting to die or killing yourself? Was it to end the pain or stop the way you were feeling (in other words you couldn't go on living with this pain or how you were feeling) or was it to get attention, revenge or a reaction from others? Or both?
 
 
 (1) Completely to get attention, revenge or a reaction from others	(4) Mostly to end or stop the pain (you couldn't go on living with the pain or how you were feeling)	
 
 (2) Mostly to get attention, revenge or a reaction from others	(5) Completely to end or stop the pain (you couldn't go on living with the pain or how you were feeling)	
 
 (3) Equally to get attention, revenge or a reaction from others and to end/stop the pain	(0) Does not apply	
 
		(1) Completely to get attention, revenge or a reaction from others	(4) Mostly to end or stop the pain (you couldn't go on living with the pain or how you were feeling)	(2) Mostly to get attention, revenge or a reaction from others	(5) Completely to end or stop the pain (you couldn't go on living with the pain or how you were feeling)	(3) Equally to get attention, revenge or a reaction from others and to end/stop the pain	(0) Does not apply	_____
(1) Completely to get attention, revenge or a reaction from others	(4) Mostly to end or stop the pain (you couldn't go on living with the pain or how you were feeling)							
(2) Mostly to get attention, revenge or a reaction from others	(5) Completely to end or stop the pain (you couldn't go on living with the pain or how you were feeling)							
(3) Equally to get attention, revenge or a reaction from others and to end/stop the pain	(0) Does not apply							

SUICIDAL BEHAVIOR (Check all that apply, so long as these are separate events; must ask about all types)		Since Last Visit
Actual Attempt: A potentially self-injurious act committed with at least some wish to die, as a result of act. Behavior was in part thought of as method to kill oneself. Intent does not have to be 100%. If there is any intent/desire to die associated with the act, then it can be considered an actual suicide attempt. There does not have to be any injury or harm , just the potential for injury or harm. If person pulls trigger while gun is in mouth but gun is broken so no injury results, this is considered an attempt. Infering Intent: Even if an individual denies intent/wish to die, it may be inferred clinically from the behavior or circumstances. For example, a highly lethal act that is clearly not an accident so no other intent but suicide can be inferred (e.g., gunshot to head, jumping from window of a high floor/story). Also, if someone denies intent to die, but they thought that what they did could be lethal, intent may be inferred. Have you made a suicide attempt? Have you done anything to harm yourself? Have you done anything dangerous where you could have died? What did you do? Did you _____ as a way to end your life? Did you want to die (even a little) when you _____? Were you trying to end your life when you _____? Or Did you think it was possible you could have died from _____? Or did you do it purely for other reasons/ without ANY intention of killing yourself (like to relieve stress, feel better, get sympathy, or get something else to happen)? (Self-Injurious Behavior without suicidal intent) If yes, describe:		Yes  No  Total # of Attempts _____
Has subject engaged in Non-Suicidal Self-Injurious Behavior? Interrupted Attempt: When the person is interrupted (by an outside circumstance) from starting the potentially self-injurious act (if not for that, actual attempt would have occurred). Overdose: Person has pills in hand but is stopped from ingesting. Once they ingest any pills, this becomes an attempt rather than an interrupted attempt. Shooting: Person has gun pointed toward self, gun is taken away by someone else, or is somehow prevented from pulling trigger. Once they pull the trigger, even if the gun fails to fire, it is an attempt. Jumping: Person is poised to jump, is grabbed and taken down from ledge. Hanging: Person has noose around neck but has not yet started to hang - is stopped from doing so. Has there been a time when you started to do something to end your life but someone or something stopped you before you actually did anything? If yes, describe:		Yes  No  Total # of interrupted _____
Aborted Attempt: When person begins to take steps toward making a suicide attempt, but stops themselves before they actually have engaged in any self-destructive behavior. Examples are similar to interrupted attempts, except that the individual stops him/herself, instead of being stopped by something else. Has there been a time when you started to do something to try to end your life but you stopped yourself before you actually did anything? If yes, describe:		Yes  No  Total # of aborted _____
Preparatory Acts or Behavior: Acts or preparation towards imminently making a suicide attempt. This can include anything beyond a verbalization or thought, such as assembling a specific method (e.g., buying pills, purchasing a gun) or preparing for one's death by suicide (e.g., giving things away, writing a suicide note). Have you taken any steps towards making a suicide attempt or preparing to kill yourself (such as collecting pills, getting a gun, giving valuables away or writing a suicide note)? If yes, describe:		Yes  No 
Suicidal Behavior: Suicidal behavior was present during the assessment period?		Yes  No 
Suicide:		Yes  No 
Answer for Actual Attempts Only		Most Lethal Attempt Date:
Actual Lethality/Medical Damage: 0. No physical damage or very minor physical damage (e.g., surface scratches). 1. Minor physical damage (e.g., lethargic speech; first-degree burns; mild bleeding; sprains). 2. Moderate physical damage, medical attention needed (e.g., conscious but sleepy, somewhat responsive; second-degree burns; bleeding of major vessel). 3. Moderately severe physical damage, medical hospitalization and likely intensive care required (e.g., comatose with reflexes intact; third-degree burns less than 20% of body; extensive blood loss but can recover; major fractures). 4. Severe physical damage, medical hospitalization with intensive care required (e.g., comatose without reflexes; third-degree burns over 20% of body; extensive blood loss with unstable vital signs; major damage to a vital area). 5. Death		Enter Code _____
Potential Lethality: Only Answer if Actual Lethality=0 Likely lethality of actual attempt if no medical damage (the following examples, while having no actual medical damage, had potential for very serious lethality: put gun in mouth and pulled the trigger but gun fails to fire so no medical damage, laying on train tracks with oncoming train but pulled away before run over). 0 = Behavior not likely to result in injury 1 = Behavior likely to result in injury but not likely to cause death 2 = Behavior likely to result in death despite available medical care		Enter Code _____

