2. SCHEDULE OF EVENTS

Assessments	Screening Day -14 to -11	Day 0 Treatment Day 0	Wk 2 Day 14 ±3 days	Wk 4 Day 28 ± 3 days	Wk 8 Day 56 ± 3 days	Wk 12 Treatment Day 84 ± 3 days	Wk 24 Treatment Day 168 ± 3 days	Wk 36 Treatment Day 252 ± 3 days	Wk 48 Treatment Day 336 - 7/+ 14 days	Wk 60 Treatment Day 420 ± 7 days	Wk 72 Treatment Day 504 ± 7 days	Wk 84 Treatment Day 588 ± 7 days	Wk 56 ⁹ or 104 End of Trial / Early Withdrawal Day 392 or 728 ± 7 days
Informed Consent	X												
In/Ex Criteria	X	X											
Demographics	X												
Medical History	X												
Height	X												
Weight	X	X				X	X	X					X
Physical Exam ¹	X	X				X	X	X	X ¹¹	X	X	X	X
Vital Signs ³	X	X				X	X	X	X	X	X	X	X
C-SSRS ^{4,1}	X	X	X	X	X	X	X	X	X	X	X	X	X
Patient Global Impression of Change (PGIC) ²				X	X	X	X	X	X	X	X	X	X
SF-36, HIT-6 ¹	X	X		X		X	X	X	X	X	X	X	X
EQ-5D-5L ¹²	X	X		X		X	X	X	X				X ¹⁰
Most Bothersome Symptom (MBS)	X	X		X	X	X	X	X	X				X ¹⁰
MIDAS ¹		X				X	X	X	X	X	X	X	X
AE Review	X	X	X	X	X	X	X	X	X	X	X	X	X
Concomitant Meds Review	X	X	X	X	X	X	X	X	X	X	X	X	X
ALD403 infusion ⁵		X				X	X	X	X ¹¹	X	X	X	
12-lead ECG ⁷	X	X				X	X	X	X	X	X	X	X
Hematology, Chemistry ¹	X	X				X	X	X	X	X	X	X	X
HIV/Hepatitis B and C	X												
Plasma PK ^{8,8}		X	X	X	X	X	X	X	X		X		X
Serum Anti-ALD403 ⁶		X	X	X	X	X	X	X	X		X		X
Urine Drugs of Abuse Screen	X												
Urine Pregnancy (hCG) Test ¹	X	X		X	X	X	X	X	X	X	X	X	X

¹ Conduct assessment pre-dose on Day 0 and Week 12, 24, 36, 48, 60, 72, and 84.

² Conduct assessment pre-dose on Week 12, 24, 36, 48, 60, 72, and 84.

³ Conduct assessments pre-dose and up to 2 hours (+ 30 min) post-dose on Day 0 and Week 12, 24, 36, 48, 60, 72, and 84.

⁴ Conduct C-SSRS Baseline/Screening Version at screening and C-SSRS Since Last Visit Version at remaining visits where C-SSRS required.

⁵ Monitor subjects for at least 2 hours after the end of each dosing to assess for the occurrence of adverse events.

⁶ Collect samples pre-dose on Day 0 and Week 12, 24, 36, 48, and 72. Subjects who test positive for anti-ALD403 antibodies at the last study visit will be asked to provide up to 2 additional blood samples for immunogenicity testing at approximately 3 month intervals for up to 6 months.

⁷ Conduct assessment pre-dose, and within 2 hours (+30 min) post dose on Day 0 and Week 12, 24, 36, 48, 60, 72, and 84.

⁸ On Day 0, collect additional sample immediately post-dose (within 15 minutes of end of infusion).

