12. Any clinically significant concurrent medical condition or clinically significant laboratory abnormality at screening or on Day 0.

13. Body Mass Index (BMI) ≥ 39 kg/m² at screening.

14. The subject is at risk of self-harm or harm to others in the investigator's opinion, based on clinical interview and responses provided on the Columbia-Suicide Severity Rating Scale (C-SSRS). Subjects must be excluded if they have a lifetime history of a serious suicide attempt or multiple suicide attempts (i.e., actual, interrupted, or aborted attempts), had any suicidal behavior in the past 5 years (i.e., preparatory acts or behavior), or had suicidal ideation of Type 3, 4 or 5 (i.e., suicidal ideation with any method without intent to act or suicidal ideation with intent to act, with or without a plan), in the past 6 months, as measured by the C-SSRS at screening or on Day 0.

15. Any history or evidence of substance abuse or dependence (e.g., alcohol, opiates, amphetamines, and barbiturates) within the past 2 years according to the International Classification of Diseases (ICD) 10: F10-19.

16. Pregnant, breastfeeding, or planning to become pregnant during the trial.

17. Receipt of any experimental, unregistered therapy (within or outside a clinical trial)

within 30 days or 5 plasma half-lives (whichever is longer) before screening.

18. Planned or current participation in any other clinical trial for the duration of this clinical trial, or within 6 months prior to screening. NOTE: Subjects who participated in prior clinical trials of CGRP antagonists, including ALD403-CLIN-005, may be eligible to participate if they
 - had their last dose of study drug more than 6 months prior to screening, AND
 - had no clinically significant adverse events related to study drug during their participation in the prior trial as assessed by the Investigator prior to enrollment.
19. Recent or planned surgery, requiring general anesthesia, within 8 weeks prior to screening and during the duration of this clinical trial.
20. Positive for HIV, hepatitis B surface antigen, or hepatitis C antibody at screening.
21. Any condition that, in the opinion of the investigator, would make the subject unsuitable for the clinical trial.
22. Employees of Alder, the CRO(s), or any clinical trial site involved in this trial and their immediate family members (i.e., parents, spouse, siblings, children).

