13.4.4.6. C-SSRS

The C-SSRS assesses lifetime suicidality during an initial baseline evaluation, and then monitors suicidal ideation and suicidal behavior at subsequent follow-up assessments. Four constructs are measured. The first and second are the severity and intensity of ideation, rated on a 5-point ordinal scale. The third is the behavior subscale, which is rated on a nominal scale and the fourth is the lethality subscale, which assesses actual attempts. These results will be reported at baseline and post baseline. Results for individual time points will be provided in a listing.

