3.4.5 Headache Impact Test (HIT-6)

The actual score and change from baseline in the total score will be summarized using the Safety Population at each scheduled visit. A shift from baseline to each scheduled visit will be tabulated. Testing of the change from baseline results will be performed at Weeks 12, 24, 36, 48, 60, 72, 84 and Week 104. T-tests will be performed based upon the change in total score.

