3.6.6 Columbia-Suicide Severity Rating Scale (C-SSRS)

The C-SSRS assesses lifetime suicidality during an initial baseline evaluation, and then monitors suicidal ideation and suicidal behavior at subsequent follow-up assessments. Four constructs are measured. The first and second are the severity and intensity of ideation, rated on a 5-point ordinal scale. The third is the behavior subscale, which is rated on a nominal scale and the fourth

is the lethality subscale, which assesses actual attempts. These results will be reported at baseline and post baseline. Results for individual time points will be provided in a listing.

The denominator for percentages will be the number of subjects with a C-SSRS assessment at baseline or at any time post baseline. The post baseline summary will list a subject as yes if they ever selected yes after baseline.

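### The planned post-baseline C-SSRS summary counts recurring Type 1–2 (or older) ideation the same as new ideation, because it is never compared with the subject's own pre-dose level

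*Protocol*

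**What the plan says.** SAP 3.6.6 names four C-SSRS constructs (severity of ideation, intensity of ideation, behavior, lethality) and sets out the reporting: "These results will be reported at baseline and post baseline. Results for individual time points will be provided in a listing". Percentages use this base: "The denominator for percentages will be the number of subjects with a C-SSRS assessment at baseline or at any time post baseline". The post-dose rule is: "The post baseline summary will list a subject as yes if they ever selected yes after baseline". Protocol 13.4.4.6 has the same reporting sentence ("These results will be reported at baseline and post baseline") without the rule for an ever-yes answer. Neither document plans a C-SSRS shift table or defines new or worsened ideation.

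The forms are set by a footnote to the protocol's Schedule of Events: "Conduct C-SSRS Baseline/Screening Version at screening and C-SSRS Since Last Visit Version at remaining visits where C-SSRS required". The screening form (Protocol 15.2.1) has a lifetime column and a past-6-months column for ideation. The later form (15.2.2) has one column, for the interval since the last visit; its first item reads "Subject endorses thoughts about a wish to be dead or not alive anymore, or wish to fall asleep and not wake up".

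Exclusion 14 (Protocol 8.2) removes subjects who "had suicidal ideation of Type 3, 4 or 5" within 6 months, as measured at screening or on Day 0. For other endpoints the SAP does compare each subject with baseline. For HIT-6, for example: "A shift from baseline to each scheduled visit will be tabulated". Shifts are also planned for MIDAS, the EQ-5D-5L items and laboratory values.

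**The concern.** Safety is the primary objective, the C-SSRS is one of five named safety endpoints, and there is no control arm. The only internal reference for an ideation answer after dosing is what the same subject reported before dosing. The SAP respects this for adverse events, where treatment-emergent is defined by onset, and for the shift tables above, but not for the C-SSRS.

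A reader of the final tables would see a baseline percentage and a post-baseline percentage. From these they could not say how many subjects had ideation that was new, how many had a recurrence, and how many moved up the scale at the low end.

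**Working it through.** **1. Who can enter with prior ideation.** The ideation clause of exclusion 14 covers Types 3–5 within 6 months. It leaves in subjects with Type 1 or 2 in that period, and subjects whose Type 3–5 ideation is older. The investigator's judgement of self-harm risk and the suicidal-behavior clauses may remove some of these, but not as a rule about ideation type.

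**2. What each kind of change looks like in the planned output.** The recent level is the one in the past 6 months. The table assumes rows by ideation type, which the SAP implies by reporting severity but does not state.

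| Recent level → worst post-dose | C-SSRS summary | Adverse event route | Identified as new or worse? |
|---|---|---|---|
| 1 or 2 → same type | yes | not mandatory | Recurrence; looks like a first occurrence |
| None → 1 or 2 | yes | not mandatory | No, only from the listing |
| 1 → 2 | yes | not mandatory | No, only from the listing |
| None, 1 or 2 → 3 | yes on question 3 | possible under Protocol 11.1.2, not required by 11.1.9 | Yes, because exclusion 14 bars recent Type 3 |
| None, 1 or 2 → 4 or 5 | yes on question 4 or 5 | mandatory under 11.1.9 | Yes |

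If the Type 3–5 ideation is a return of something older than 6 months, it is above the recent level but not a first occurrence. The planned summary does not show that either.

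**3. Whether the two percentages side by side solve it.** They do not. With b subjects yes before dosing and a subjects yes after, out of N, the number newly yes can lie anywhere from max(0, a − b) to min(a, N − b). As a hypothetical case with N = 120, b = 12 and a = 8, that is from max(0, −4) = 0 to min(8, 108) = 8.

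**4. Which visit is the baseline.** SAP 3.2 takes the last value before dosing, generally Day 0. The Day 0 form looks back only to screening, 11 to 14 days earlier. SAP 3.6.6, however, describes an initial baseline evaluation of lifetime suicidality, which is the screening form. Under the Day 0 reading, a subject with Type 1 ideation three months before screening, none since, and a recurrence at Week 24 would read no, then yes. The SAP does not say which form applies.

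**5. Illustrative size.** The documents contain no C-SSRS rate, so there is no figure to reproduce and every rate here is an assumption. Let p be the share of 120 subjects entering with Type 1–2 ideation (2% to 10%), r the share of those who report it again (30% to 70%), and q the share of the others with new ideation (1% to 3%). The count is of subjects with any yes.

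- Recurring = 120 × p × r; new = 120 × (1 − p) × q.
- Lowest total (p = 2%, r = 30%, q = 1%): 0.72 + 1.18 = 1.9 subjects, 38% of them recurring.
- Highest total (p = 10%, r = 70%, q = 3%): 8.40 + 3.24 = 11.6 subjects, 72% recurring.
- Lowest recurring share (p = 2%, r = 30%, q = 3%): 0.72 / 4.25 = 17%.
- Highest recurring share (p = 10%, r = 70%, q = 1%): 8.40 / 9.48 = 89%.

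Across the grid, the new cases number 1.1 to 3.5.

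**The case against.** The strongest reply is that the serious cases are already covered. A reader might infer that worsening is not counted at all. The documents do not support that: for an eligible subject any post-dose yes to questions 3–5 exceeds the past-6-months level and appears as a yes. Questions 4 and 5 and any behavior item must also be reported as adverse events, and suicidality terms are tabulated as events of special interest in SAP 3.6.2.1.

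A reader might also infer that Type 3 ideation is kept out of the adverse event tables. It is not. Protocol 11.1.9 does not require it to be reported, but Protocol 11.1.2 covers new or worsened conditions and clinically significant findings, so an investigator can report it. That route does separate new from unchanged, though it depends on judgement rather than on the scale.

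Three further points stand. The row is called post baseline, not treatment-emergent, so it misleads only a reader who takes it as such. The listing allows reconstruction by hand. And a shift table has its own bias: it sets roughly 6 months (26 weeks) plus 2 weeks of screening, about 28 weeks, against up to 104 weeks after dosing, or 104 / 28 = 3.7 times as long. The longer window favours apparent worsening with no drug effect.

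These points limit the concern to recurrence and to movement within none, Type 1 and Type 2. They do not supply the missing within-subject comparison there.

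**Conclusion.** The gap is real and limited. On a named safety endpoint in an uncontrolled trial, the post-baseline summary cannot separate recurring from new ideation at Types 1–2, cannot show that a Type 3–5 answer is a return of older ideation, and does not identify movement from none to Type 1–2 or from 1 to 2. The C-SSRS baseline is also unclear between the screening form and Day 0.

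Its size cannot be established from the documents. The 17% to 89% share is an illustration resting wholly on assumed rates, and no particular degree of overstatement should be claimed from it. Nor is the form at fault: asking about the time since the last visit is adequate once the answers are linked to the screening form. This is an inexpensive improvement to reporting, not a threat to the trial's conclusions on serious suicidality.

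**What to change.** Amend SAP 3.6.6 as follows:

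- Define the C-SSRS pre-dose level as the worst ideation type (0 for none, then 1–5) across the past-6-months column of the screening form and the Day 0 form, and state that this replaces the general baseline rule of SAP 3.2 for the ideation comparison.
- Add a subject-level shift table of that level against the worst type on any post-dose form, among subjects with both.
- Define new ideation as a move from 0 to any type, and worsened ideation as a move from one type to a higher one; report n (%) for each.
- Show the worst lifetime type alongside, so that a return of older ideation can be recognised.
- Label the existing ever-yes rows as including pre-existing ideation.
- Footnote the unequal look-back (about 6 months before dosing, up to 104 weeks after) and state that the table is descriptive and not evidence of a drug effect.

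The cost is one table and a few lines of SAP text. All the data are already collected, and neither the protocol nor subject management changes.
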